7.4 PHARMACOKINETIC ANALYSES

Plasma samples will be analyzed for IPI-145 and potential metabolite concentrations using a validated high performance liquid chromatography-tandem mass spectrometry (LC/MS/MS) method. A summary table and a listing of IPI-145 and IPI-656 concentrations will be provided. The PK data collected will be analyzed by standard population PK methods, using appropriate software. Analysis of exposure-response relationships for efficacy and safety endpoints will be conducted. If there is only a limited amount of plasma concentration data from this study, the data may be pooled with the results of other studies to perform the population PK and exposure-response analyses. Further details on these analyses will be outlined in a separate analysis plan.

Results of the population PK and exposure-response analysis will be summarized in a separate technical report.

7.5 BIOMARKER ANALYSES

Biomarkers measured in serum, plasma, blood and tumor tissues will be analyzed in an exploratory fashion. These exploratory analyses may or may not be presented formally. If presented, they will be limited to biomarkers for which data from a sufficient number of subjects are available.

7.6 QOL ANALYSES

EQ-5D data will be summarized for the FAS by visit. The number and percentage will be presented for each question/domain, and summary statistics will be provided for the health status score.

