- m. Complete urinalysis with qualitative analysis for protein will be performed at Screening, at Cycle 3, Day 1 and at Cycle 7, Day 1. Positive results (protein >30 mg/dL) will require quantitative analysis (assessment of urine protein to creatinine ratio) if not previously noted as part of medical history. Clinically significant laboratory findings including but not limited to those resulting in a drug interruption/reduction/discontinuation or requiring medical intervention should be reported as an adverse event (see protocol [Section 8.1.1](#) for definition of an AE).
- n. For a period of 14 days prior to Cycle 1 Day 1 and throughout study treatment, subjects must avoid the concomitant use of drugs or foods that are strong inducers and inhibitors of CYP3A4. Moderate or weak inducers/inhibitors may be used with caution (See Appendix 2).
- o. Prior/concomitant procedures should include all transfusions. If the subject is transfusion-dependent at Screening, transfusion history from the previous 3 months will be collected.
- p. Adverse events will be collected from time of informed consent through the 30-day post-treatment visit for all subjects (excluding screen failures). SAEs will be collected from the time of informed consent (including screen failures) through 30 days after the last dose of study drug for all subjects. All AEs will be followed until resolution, return to baseline or it is determined the event is considered chronic. See [Section 8.1.1](#) of the protocol for more information regarding AE/SAE collection and reporting.
- q. Quality of life assessment includes the EQ-5D questionnaire. Conducted at Screening, and on Day 1 of Cycle 3, Cycle 5, Cycle 7, and Cycle 10, and Day 1 of every 4th cycle thereafter while on treatment (i.e. Cycle 14, 18, 22, etc.), and, when possible, at End of Treatment (EoT) (if >1 months from last administered questionnaire).
- r. IPI-145 capsules will be administered twice daily (BID) in 28-day cycles. IPI-145 doses will be dispensed at a minimum monthly through Cycle 8 and every two months thereafter so the subject has enough IPI-145 doses until at least the next dispensation visit, taking into account the dispensation visit window. The ± 4 day window for Day 1 in relevant Cycles does not apply to dose administration as dosing is daily. Doses should be taken every 12 hours within ± 2 hours of the scheduled dose. Missed doses outside this window or vomited doses should not be taken or repeated.

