2.3 EXPLORATORY OBJECTIVES

The exploratory objectives of the study are:

- To evaluate whether baseline values or treatment-related changes in biomarkers correlate with IPI-145 clinical activity, safety and/or resistance in iNHL.
- To evaluate whether tumor genomic or pharmacogenomic markers correlate with IPI-145 clinical activity, safety, PK and/or resistance in iNHL
- To evaluate the health-related quality of life (QoL) of subjects

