6.3.9 Subject-reported Outcomes Assessment

Subject self-reported health related quality of life will be assessed at Screening, on Day 1 of Cycle 3, Cycle 5, Cycle 7, and Cycle 10, and Day 1 of every 4th Cycle thereafter while on treatment (i.e., Cycle 14, 18, etc.), and, when possible, upon treatment discontinuation for any reason. Subject-reported health-related quality of life will be assessed using the EQ-5D questionnaire. An English-language example of this instrument is shown in Appendix 6.

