9.7.2 Analyses of Health-Related QoL

Details on the analysis methods of health-related QoL endpoints will be provided in the SAP.

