6.7 VISIT WINDOWS

Unless otherwise specified, the baseline value is defined as the most recent value prior to first study drug administration.

Treatment visits, cycles, and days are pre-defined for this study and are pre-specified on the CRF. In the presentation of study data using Study Day and Cycle Day, the following derivations will be used:

- Day 1 of Study = Date of first dose for a subject
- Study Day = Date – Date of first dose + 1, if Date is on or after Date of first dose; or Study Day = Date – Date of first dose, if Date is before Date of first dose
- Day 1 of Cycle = Date of cycle start, as reported on eCRF (per protocol, Day 1 of Cycle 1 should be Day 1 of Study)
- Cycle Day = Date – Date of cycle start in current cycle + 1

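### EQ-5D is summarised only by visit, with no within-subject change, so the planned table has limited ability to separate a change in quality of life from a change in who is still measured

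*SAP*

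**What the plan says.** Quality of life is an exploratory objective (Protocol 2.3): "To evaluate the health-related quality of life (QoL) of subjects". Protocol 9.7.2 leaves the method to the SAP: "Details on the analysis methods of health-related QoL endpoints will be provided in the SAP".

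SAP 7.6 is the whole of that method. First, "EQ-5D data will be summarized for the FAS by visit". Then, "The number and percentage will be presented for each question/domain, and summary statistics will be provided for the health status score". It names no change from baseline, shift table, completion rate or rule for missing questionnaires. SAP 6.2 deals only with partial dates, and SAP 6.1 adds that continuous variables are shown with the number of non-missing values.

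Collection is at Screening, then Day 1 of Cycles 3, 5, 7 and 10, then "Day 1 of every 4th Cycle thereafter while on treatment (i.e., Cycle 14, 18, etc.), and, when possible, upon treatment discontinuation for any reason" (Protocol 6.3.9). The quality-of-life footnote to Protocol Table 1 restricts the last questionnaire further: "and, when possible, at End of Treatment (EoT) (if >1 months from last administered questionnaire".

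A baseline is available. SAP 6.7 says that "the baseline value is defined as the most recent value prior to first study drug administration", which for EQ-5D is the Screening questionnaire.

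**The concern.** The subjects behind each row of the table are not the same people. Protocol 4.4 takes subjects off treatment for progression, for adverse events requiring permanent discontinuation, and at death. Protocol 4.1 and 4.3 let only subjects with CR, PR or SD continue past Cycle 13. The Cycle 14 and later rows therefore describe mainly subjects who have not progressed and who tolerated the drug.

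If the subjects who left had worse scores from the start, the by-visit mean rises as they go, and the share reporting no problems in a domain rises with it. Someone reading across the visits could take that for benefit. In a single-arm trial there is no comparator in which the same drift would show up, so within-subject change from Screening is the natural internal reference. The plan collects what is needed for it but does not tabulate it.

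What is at stake is the interpretation of one exploratory endpoint.

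**Working it through.** The documents give no EQ-5D mean, SD, effect size or dropout rate, so there is no planned figure to reproduce. All numerical inputs below are assumptions.

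**1. Size of the compositional drift**

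Let *f* be the fraction who have left by a visit, *g* the baseline gap (stayers minus leavers), *m* the stayers' baseline mean, and 70 the baseline mean of everyone. No subject changes.

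(1 − f)·m + f·(m − g) = 70, so m = 70 + f·g.

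With f = 0.4:
- g = 5: m = 70 + 2 = 72
- g = 10: m = 70 + 4 = 74
- g = 15: m = 70 + 6 = 76

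With g = 10, f = 0.30 gives a rise of 3 points and f = 0.67 a rise of 6.7. If g = 0 there is no rise, and if g is negative the drift is downward.

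The documents do not fix *f*. Protocol 1.3.3.2 reports a median of 9.8 treatment cycles for iNHL subjects at 25 mg BID in Study IPI-145-02, while Protocol 1.5 gives 4.7 for what appears to be the same group. In addition, 42% of all subjects in that study were still on treatment at the data cut, so neither median can be read as a dropout rate.

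**2. What the added columns would show**

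The movement from the overall Screening mean to a visit mean splits exactly, among subjects with both values:

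(visit mean − overall Screening mean) = (visit mean − same subset's Screening mean) + (same subset's Screening mean − overall Screening mean).

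The first term on the right is the paired change and the second is the change in who is measured. In the 10-point illustration, 74 − 70 = (74 − 74) + (74 − 70) = 0 + 4. The planned table shows 70 and 74, but neither term.

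**3. Does paired change remove the bias?**

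This was simulated with assumed inputs: mean 70, SD 20, no true change, within-subject correlation 0.5 or 0.7, and retention of 85, 70, 58, 45 and 33% at Cycles 3, 5, 7, 10 and 14. Dropout depended on the score named below plus random noise of equal variance, which is strong selection. Results at Cycle 14, as correlation 0.5 / 0.7:

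| Dropout depends on | By-visit mean | Mean paired change |
|---|---|---|
| Nothing (random) | 70.0 / 70.0 | 0.0 / 0.0 |
| Stable health level | 82.8 / 85.0 | 0.0 / 0.0 |
| Observed Screening score | 79.0 / 82.6 | −9.1 / −5.5 |
| Previous score | 80.4 / 83.6 | −1.1 / −0.5 |
| Current score | 83.6 / 85.5 | +3.3 / +2.0 |

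With lighter attrition (70% retained at Cycle 14, correlation 0.6), the by-visit mean was 76.3 for dropout on stable health and 76.4 for dropout on current score. The paired changes were 0.0 and +1.2.

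Under health-related dropout the spurious by-visit rise was about 6 to 15 points. Paired change removes it fully when dropout follows a stable health level. When dropout follows the observed Screening score, regression to the mean produces an apparent decline. When it follows the current score, some upward bias remains.

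**The case against.** **Nothing in the documents links EQ-5D to dropout.** This stands. A reader might infer that the table will show improving quality of life. The documents do not support that: with random dropout there is no drift, and a real fall in quality of life, for example from toxicity, could cancel it. That leavers were worse off is a reasonable inference from the reasons for leaving, but it remains an inference.

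**The attrition is visible.** SAP 6.1 puts the shrinking count beside each mean, and SAP 7.1.1 tabulates reasons for discontinuation. This is true and tempers the point. Neither shows whether the remaining subjects started with better scores.

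**The objective is not worded as change.** This stands. A reader might infer that the planned table cannot address the objective. That goes too far: the objective is to evaluate quality of life, no test is planned, and a by-visit description that includes Screening and available end-of-treatment questionnaires does so with limits.

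**SAP 7.3 plans change from baseline for ECG and immunoglobulins.** A reader might take its absence for EQ-5D as an internal inconsistency. It is not one. Protocol 3.2 defines the laboratory endpoint as changes in values, and Protocol 9.5 has ECG measurements tabulated for changes over time. The quality-of-life endpoint has no such wording.

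**The end-of-treatment questionnaire captures leavers.** This holds only in part. It is conditional, and it forms its own row without altering the on-treatment rows.

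**Paired change is not a full cure.** This stands, as step 3 of the working shows.

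**Conclusion.** The concern holds as a limitation of the planned EQ-5D table. By-visit summaries of subjects still on treatment can drift upward with no subject improving, provided those who leave had worse quality of life. The size is the dropout fraction times the baseline gap: 2 to 6 points for 40% attrition and gaps of 5 to 15 points, all assumed. The simulated 6 to 15 points rest on strong assumed selection and are not a forecast. The direction is conditional, because random dropout gives zero and a true decline could mask the drift.

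The weight is low. EQ-5D is exploratory and descriptive, no decision depends on it, and the ORR analysis is untouched. The change is worth making because it costs almost nothing and uses data already collected.

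**What to change.** In SAP 7.6 keep the by-visit summary and add, for each post-baseline visit and for end of treatment:

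- the paired change from Screening in the health score, among subjects with both values;
- the Screening mean of that same subset, next to its visit mean;
- a shift table from Screening for each EQ-5D domain in the same subset;
- the number of questionnaires expected and completed. Expected could be defined as subjects on treatment at that visit and, for end of treatment, subjects who discontinued more than one month after their last questionnaire.

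Add one sentence stating that the paired change is descriptive and does not remove bias from informative dropout or regression to the mean.

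The cost is a few lines of SAP text and one more exploratory table. There is no added data collection or patient burden, and no effect on the primary analysis.

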8 CHANGES IN PLANNED ANALYSES

8.1 CHANGES IN PLANNED ANALYSES FROM PROTOCOL AMENDMENT 1 TO SAP V1.0

No change is made in the planned analyses from protocol amendment 1 to SAP V1.0.

8.2 CHANGES IN PLANNED ANALYSES FROM SAP V1.0

SAP Version	Section	Summary of Change	Reason for Change
2.0	3.2	Change the number of FL subjects	Update per Protocol Amendment 2
2.0	3.4	Change internal DMC to external IDMC	Update per Protocol Amendment 2
2.0	5.3	Remove CR as an exploratory endpoint	Update per Protocol Amendment 3
2.0	6.5	Definition of refractory	Be consistent with entry criteria
2.0	6.5	Add additional subgroup analysis for the primary endpoint	Better understand the performance of Duvelisib
2.0	7.1.4	Add analysis of specific prior therapies	Better characterise patient population
2.0	7.2.2.3	Add analysis of OS rate at 12 months	Needed as the median may not be available at the time of primary analysis
2.0	7.2.2.4	Change the analysis method for TTR	TTR can be summarized descriptively as no censoring is involved
2.0	7.3.2	Change the presentation of some lab data	Better present lab data

10 APPENDIX

Appendix 1 Summary of Laboratory Parameters and Associated Normal Ranges

Lab Type	Parameter	Textbook Reference Range	Unit
Hematology	WBC/Leukocytes*	4.5-11.0	10 ³ /uL
	Hemoglobin*	Male: 13.5-17.5 Female: 12.0-16.0	g/dL
	Hematocrit	Male: 41.00-53.00 Female: 36.00-46.00	%
	Platelets*	150-350	10 ³ /uL
	Lymphocytes	22-44	%
	Neutrophils	40-70	%
	Eosinophils	0-8	%
	Monocytes	4-11	%
	Basophils	0-3	%
	Lymphocytes*	1.2-3.4	10 ³ /uL
	Neutrophils*	3-5.8	10 ³ /uL
	Eosinophils	0-0.7	10 ³ /uL
	Monocytes	0.11-0.59	10 ³ /uL
	Basophils	0-0.2	10 ³ /uL
	ANC*	3-5.8	10 ³ /uL
Blood Chemistry	Glucose*	75.00-115.00	mg/dL
	BUN	10.00-20.00	mg/dL
	Serum creatinine*	0-1.5	mg/dL
	Sodium*	136-145	mEq/L
	Potassium*	3.5-5.0	mEq/L
	Chloride	98-106	mEq/L
	Bicarbonate	21-30	mEq/L

	Carbon dioxide	21-30	mEq/L
	Calcium*	9.0-10.5	mg/dL
	Total Protein	5.5-8.0	g/dL
	Albumin*	3.5-5.5	g/dL
	Phosphorus*	3.0-4.5	mg/dL
	Magnesium*	0.74-1.23	mmol/L
	Lipase*	0-160	U/L
	Amylase*	60-180	U/L
	Uric acid*	Male: 2.5-8.0 Female: 1.5-6.0	mg/dL
Liver Function Tests	ALT(SGPT)*	0-35	U/L
	AST(SGOT)*	0-35	U/L
	Alkaline phosphatase*	30-120	U/L
	Direct bilirubin	0.10-0.30	mg/dL
	Total Bilirubin*	0.30-1.00	mg/dL
	LDH	100-190	U/L
Coagulation	PT	11.1-13.1	sec
	aPTT*	22.1-35.1	sec
	INR*	0.9-1.1	No Unit
Immunoglobulins	IgA	60-309	mg/dL
	IgE	10-179	IU/mL
	IgG	614-1295	mg/dL
	IgM	53-334	mg/dL

*Indicates CTCAE Gradable
